Experimental Group. In addition to standard medical care provided to their child, parents in the experimental group will receive online peer mentoring via the iParent2Parent Program. The iParent2Parent program is a tailored peer-mentorship program that provides modeling and reinforcement by peers (trained parents of children with JIA) to parents of children diagnosed with JIA. The program will run over 2-3 months via 5-10 weekly to bi-weekly Skype calls. [name] will identify 5-7 suitable mentors (male and female) per site who meet eligibility criteria. A member of the research team will interview interested mentors, describe the program, outline requirements, and answer any study-related questions. During mentor training, all mentors will meet with [name], a licensed psychologist, who will screen for potential psychosocial concerns and considerations when taking on the role of a mentor (e.g., the personal impact of discussing their own child's JIA, speaking with other parents who have a child with JIA). Efforts will be made to pair mentors and mentees who share similar characteristics (e.g., sex/gender) as well as their child's characteristics (e.g., age, diagnosis). During the study period, mentors may be assigned up to 3 mentees at any time. The total number of mentees a peer mentor takes on is their choice. Mentees may be from either SickKids or IWK Health Centre. Before assigning a mentee, the research coordinator will reach out to the peer mentor to discuss additional commitment and assign mentees based on availability and willingness of mentors. A research assistant (RA) at each participating site will facilitate initial Skype calls. Dyads will be responsible for scheduling remaining calls at mutually agreeable times (same time each week with flexibility to schedules). Mentors and mentees may coordinate future calls via Skype or email. If participants cannot complete the iPeer2Peer intervention via Skype (e.g., no access to computer and/or internet), a phone option will be made available for participants to take part in the program.

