Parent Mentor Training. Parent mentor training will involve a stepwise approach including both self-directed in-home training and one full day of in-class training facilitated by a psychologist [name] and social worker [name]. In-class training will comprise of lectures, active group discussions, small group activities, and role-play activities. iParent2Parent call topics will be decided by the mentor and mentee. However, the training manual will include suggested topics,

advice on structuring conversations, and guides to redirect conversations. Based on the evidence on parent outcomes (6-8), training will emphasize active listening, fostering adaptive coping, and problem-solving skills. Peer mentors will have access to research staff for additional training and support throughout the duration of the study if needed. This includes consultations with research staff and additional training in mentorship skills.

The following study safeguards will be put in place and any adverse events will be tracked:

- Peer mentor training on confidentiality, boundaries, self-care, and when to seek support.
- Peer mentors will be assigned a study specific online account and email address to encourage appropriate boundaries between mentor and mentee.
- Peer mentor training on emergency identification and reporting using a standardized concerns checklist, appropriate services (e.g., 911), and/or the study or local health care team.
- A member of the research team will contact peer mentors at least bi-monthly to ensure mentors are comfortable in their role, not experiencing any undue stress, and to discuss any concerns with the program.
- [name] will be available to facilitate appropriate referrals as necessary via social work department at SickKids and IWK Health Centre.

Control Group. The control group will be on a waitlist and receive usual care without intervention. The iParent2Parent Program will be offered after completion of all outcome measures.

Both Groups. Primary and secondary outcome measures will be collected online from both groups at baseline, 3 months, and 6 months.

Peer Mentors. Prior to mentor training, mentors will complete baseline outcome measures. Immediately following training, mentors will complete training evaluations. At study end, mentors will complete follow-up outcome measures and participate in a focus group.

Procedure:

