- **Primary Outcome:** trial feasibility and acceptability of the iParent2Parent Program. Criteria for feasibility are based on studies previously conducted by our group and will be: accrual rate of >70%, attrition rate of <15%, technical difficulties reported by <10% of parents and mentors, adherence rate of >80%, <5% missed responses on outcome measures and high acceptability (based on qualitative analyses). Data related to the primary outcome will be recorded on investigator-developed forms. Acceptability data will be collected using semi-structured interviews with mentors and mentees at end-of-study.
- **Secondary Outcome:** determination of treatment effect estimates for mentee participants. Effect sizes will be determined for the following: QOL (PROMIS Adult Profile 25 (13), perceived social support (Short form versions of the PROMIS battery for: Social Isolation; Informational Support; and Emotional Support) (13), coping (Coping Health Inventory for Parents (CHIP)(14); and parenting stress (Parental Stress Scale (PSS) (15).
- **Exploratory Outcome:** determination of impact for peer mentors. Effect sizes will be determined for the following: QOL (PROMIS Adult Profile 25) (13), perceived social support (PROMIS Social Isolation; Informational Support; Emotional Support) (13), coping (CHIP) (14), and parenting stress (PSS) (15). Peer mentor perceived benefits and challenges will be collected qualitatively using semi-structured interviews with mentors at end-of-study. Both groups will be asked about additional peer support sought during these time periods.

Statistical Plan:

Feasibility. This project builds on previous and ongoing research conducted by the research team. Our multidisciplinary team comprises of an experienced group of investigators with extensive and collective depth of clinical and research expertise in JIA, parenting chronically ill children, eHealth, QOL, peer support, knowledge translation, qualitative analysis, and mixed methods research.

Sample Size and Recruitment. A total of 20 participants per group is suggested for recruitment in pilot studies to examine intervention feasibility (16). SickKids and IWK Health Centre see over 150 new pediatric JIA diagnoses per year. Using a conservative estimate of 75 children diagnosed in 6 months, with a 30% refusal rate (based on our previous work (17)), we will recruit 40 parents within the timeframe.

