Inherent challenges exist when developing a new program, and this has guided our decision to focus on a feasibility RCT. The iParent2Parent Program may not be suitable for all parents of children diagnosed with JIA. Some families in rural communities do not have access to sufficient Internet bandwidth to run Skype. Efforts will be made to adapt the program (e.g., allow phone participation) for all interested parents to participate. The iParent2Parent Program is also time intensive. To accommodate this potential barrier, we have included flexibility in the number of calls between mentors and mentees. There is a potential that mentor-mentee dyads are not well suited for each other. In these cases, we will re-match a mentee with a different mentor. Mentors may also choose to discontinue the program. We will over-recruit a pool of mentors to control for drop out and variability in age, gender and child subtype of JIA. We cannot guarantee our sample will be representative of the whole parent population. However, we are recruiting from two tertiary care pediatric hospitals in ethnically diverse locations that serve both urban and rural populations.

Timeline

The proposed study will be completed within 2 years.

	YEAR 1				YEAR 2			
	Q1	Q2	Q3	Q4	Q1	Q2	Q3	Q4
Pre-intervention								
Study set-up	x	x	x	x				
Program adaption	x							
Mentor recruitment				x	x			
Mentor training workshop					x			
Participant recruitment					x	x	x	
Participant data collection					x	x	x	
Intervention								
Participant data collection					x	x	x	
Post-Intervention								
Participant data collection					x	x	x	
Participant interviews/focus groups					x	x	x	
Data analysis							x	x
Control group offered intervention							x	x
Knowledge Translation								
Presentations								x
Final reports & manuscript								x
Research team meetings	x	x	x	x	x	x	x	x

Project Leverages

This project leverages collaborations and phased methodology of the successful development of the iPeer2Peer Program. The iPeer2Peer Program has, based on *patient expressed interest*, already been adopted nationally and internationally (USA: Arthritis Foundation, Ireland: iCAN). The iPeer2Peer Program has also been expanded and is being tested in pediatric samples living with cancer, inflammatory bowel disease, chronic pain, sickle cell disease, and

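### The timeline closes outcome collection in the same quarter as recruitment, so it cannot accommodate the 6-month measures the protocol requires

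*Protocol*

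**What the plan says.** The Timeline section of the protocol gives the overall duration: "The proposed study will be completed within 2 years". In its table:

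- The row "Participant recruitment" is marked in Year 2 Q1, Q2 and Q3.
- All three rows labelled "Participant data collection" (pre-intervention, intervention and post-intervention) carry the same marks, as does the row for interviews and focus groups. None is marked in Q4.
- The row "Mentor training workshop" is marked in Year 2 Q1. Mentor recruitment runs over Year 1 Q4 and Year 2 Q1.
- Data analysis and the offer of the programme to controls are marked in Year 2 Q3 and Q4.

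The follow-up schedule is under Both Groups: "Primary and secondary outcome measures will be collected online from both groups at baseline, 3 months, and 6 months". Under Control Group, on the waitlist: "The iParent2Parent Program will be offered after completion of all outcome measures". Under Experimental Group: "The program will run over 2-3 months via 5-10 weekly to bi-weekly Skype calls".

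Sample Size and Recruitment supports the target of 40 parents as follows: "Using a conservative estimate of 75 children diagnosed in 6 months", less 30% refusing. Outcomes Measures sets the feasibility criteria, which include attrition below 15% and missed responses below 5%.

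**The concern.** A schedule that enrols parents up to the end of Q3 and stops collecting at the end of Q3 leaves no room for a 6-month measure in anyone enrolled in the preceding six months. The 6-month data feed the effect-size and variance estimates meant to size the future trial, so losing them weakens one of the stated purposes of the pilot.

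The primary outcome is feasibility, judged partly on attrition and missed responses. Assessments that never fall due because the study closes could be confused with assessments that parents failed to complete. The protocol does not say how the former are to be counted. Acceptability interviews are placed at end-of-study, yet their row also closes in Q3.

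Controls are told that the programme follows their last measure. The calendar should leave room for that offer.

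**Working it through.** **Inputs.** Year 2 starts at month 12, so Q1 ends at month 15, Q2 at 18, Q3 at 21 and Q4 at 24 (Timeline). N = 40, follow-up at 3 and 6 months, programme of 2-3 months (Study Design, Both Groups, Experimental Group). Expected diagnoses 75 in 6 months, refusal 30% (Sample Size and Recruitment).

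**The plan's own figures.** 2 x 20 = 40. Consenting parents in 6 months: 75 x 0.70 = 52.5, or 52.5 / 6 = 8.75 per month. Time to reach 40: 40 / 8.75 = 4.6 months. The recruitment target is consistent with these inputs; the problem is in the calendar.

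**Cut-offs, which need no accrual assumption.**

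- Latest enrolment giving a 6-month measure by the drawn close: 21 - 6 = month 15.
- Latest enrolment giving one within two years: 24 - 6 = month 18.
- Last 6-month measure if recruitment runs to the end of Q3: 21 + 6 = month 27.

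**How many parents are affected.** Accrual is not stated, so it is assumed uniform within each scenario.

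Share lacking the measure = 1 - (close - 6 - start) / accrual duration, limited to 0-1.

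| Accrual assumed | Lacking at close of Q3 (month 21) | Lacking at close of Q4 (month 24) |
|---|---|---|
| 8.75 per month from month 12 (4.57 months) | 1 - 3/4.57 = 34%, about 14 of 40 | 0 |
| 40 over 6 months from month 12 | 1 - 3/6 = 50%, 20 of 40 | 0 |
| Even over the drawn 9 months | 1 - 3/9 = 67%, about 27 of 40 | 1 - 6/9 = 33%, about 13 of 40 |
| 8.75 per month from mid-Q1 (month 13.5) | 1 - 1.5/4.57 = 67%, about 27 of 40 | 2%, about 1 of 40 |
| Even from mid-Q1 to the end of Q3 | 1 - 1.5/7.5 = 80%, 32 of 40 | 1 - 4.5/7.5 = 40%, 16 of 40 |
| 8.75 per month from the end of Q1 (month 15) | 100%, 40 of 40 | 1 - 3/4.57 = 34%, about 14 of 40 |

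With even accrual over the drawn window, the 3-month measure is also lost for 1 - (21 - 3 - 12)/9 = 33%, about 13 of 40, at the close of Q3.

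**Set against the feasibility limits.** Suppose assessments not yet due were counted as missed. There are 40 x 3 = 120 scheduled assessments. The calendar would remove 13.75 / 120 = 11% at 8.75 per month from month 12, and (26.7 + 13.3) / 120 = 33% with even accrual over the drawn window. Both exceed 5%. If a parent without a 6-month measure were counted as lost, even the smallest share in the table, 34%, exceeds 15%.

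**Waitlist.** A control enrolled after month 18 completes the 6-month measure after month 24, beyond the Q3-Q4 window drawn for the offer. Controls enrolled in Q1 and Q2 complete it in Q3 and Q4, which matches that window.

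**The case against.** The strongest reply is that the table is a quarter-level planning chart. Follow-up is fixed per participant elsewhere, measures are completed online, and nothing says that collection will be cut off at the end of Q3. The row is visibly schematic: it marks post-intervention collection from Q1, the quarter of mentor training, although the programme takes 2-3 months. That is fair as to what would happen in practice. It does not remove the contradiction, because this is the only calendar given and it stands beside a firm statement of duration.

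Several stronger readings are tempting, and the protocol does not support them:

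- **A reader might infer that most parents would lack 6-month data.** That depends on accrual. At 8.75 per month from the first day of Q1 the share is 34%, and the last 6-month measure falls at 12 + 4.6 + 6 = month 22.6, inside two years.
- **A reader might infer that the calendar by itself fails the primary criteria.** The protocol does not say that an assessment not yet due counts as attrition, and missed responses may mean items left blank on measures that were administered. The SAP, which is not shown, may settle this. The consequence is conditional.
- **A reader might infer that a 6-month recruitment window contradicts a 9-month one.** The sample-size paragraph gives a count of diagnoses over 6 months to show that 40 is attainable; it does not fix a window. A mark means activity at some time in that quarter, so six months starting in mid-Q1 would also mark Q1-Q3.
- **A reader might infer that the study must last until the last control finishes the programme.** The text promises an offer. It does not make completion of the programme by controls part of the study duration.

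**Conclusion.** The contradiction holds and rests only on the protocol's own dates. Recruitment through Q3, collection ending in Q3, a 6-month measure in both groups and completion within two years cannot all be true. Enrolment after month 15 misses the drawn close, enrolment after month 18 misses the two-year limit, and the last measure could fall at month 27.

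The size depends on an accrual pattern that is not stated. Under the assumptions shown, 34% to 100% of parents would lack the 6-month measure if collection stopped at the end of Q3. The low end requires full-rate enrolment from the first day of the quarter in which mentors are still being recruited and trained. Effects on the attrition and missed-response criteria follow only if assessments not yet due are counted against them.

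Severity is moderate. A collection window and a duration are misstated, but the sample size, outcomes and planned analysis are not affected.

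**What to change.** Reconcile the calendar with the follow-up schedule in one of two ways:

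- **(a)** Close enrolment by the end of Year 2 Q2 (month 18) and extend post-intervention collection and interviews through Q4 (month 24), with the final analysis after that. Because the last measure may fall at month 24, say whether the two years cover outcome collection only or also analysis and reporting.
- **(b)** Keep recruitment through Q3, extend collection and interviews to month 27, move the final analysis after it, and restate the duration.

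In either case:

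- Place the waitlist offer after each control's own 6-month measure, and state that it may run past the end of outcome collection.
- State that assessments not yet due at study closure are not counted as attrition or as missed responses.

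The cost is a corrected table and duration statement, plus either a shorter enrolment window or a later analysis date, possibly with an administrative extension. No extra participants or procedures are needed.
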